## **7. PROCEDURES FOR STUDY DOCUMENTATION**

### **Informed Consent**

If consent is conducted in person, a copy of all signed informed consent forms (ICFs) will be given to the subject, and the investigator will retain the originals. Section 3 provides further details regarding the specific requirements for informed consent.

If informed consent is conducted remotely, the study team will provide a copy of the informed consent document by email or mail to give the participant ample time to read the document. The study team will go over the details of the consent and answer questions by phone or HIPAA-compliant telehealth platform (e.g., Zoom). If the participant elects to participate, the participant and study team will provide electronic signatures using DocuSign. Digital copies of the signed ICF will be given to the subject and retained by the investigator.

### **Investigator Study File**

Documentation concerning the study including, but not limited to, study protocol and any amendments, the IRB documents, study logs, monitoring activities and correspondences, and case report forms (CRFs) will be kept on-site in a secure location.

### **Monitoring and Quality Assurance**

Quality assurance procedures will include training of all study personnel, monitoring of data and reviews to verify that all elements of Good Clinical Practice (GCP) guidelines and FDA regulations are met. Monitoring will be conducted to assure that data are accurate and in agreement with source documentation; verify that consent for study has been properly obtained and documented; confirm that participants enrolled in the study meet inclusion and

exclusion criteria; monitor for safety (e.g. adverse events) and assure that all essential documentation required by GCP guidelines are appropriately filed.

### **Retention of Study Documents**

Study documents will be retained for a period of two years on-site following the completion of the study. Study documents will then be transferred to a storage facility and secured. If the investigator relocates, retires, or withdraws from the clinical study for any reason, all records required to be maintained for the study will be transferred to an agreed-upon designee, such as another investigator at the institution where the study was conducted. Medical records used for treatment purposes will be retained separately as required by state data retention laws, HIPAA and other applicable laws.

## **8. PROCEDURES FOR HANDLING ADVERSE EVENTS (AEs) AND SERIOUS ADVERSE EVENTS (SAEs)**

Due to the nature of this study, we do not expect adverse events of the same nature as might be expected if an investigational pharmaceutical were being investigated. The exercise intervention in this study includes moderate intensity aerobic physical activity that is approved by a physician, which is likely to not include a physiological adverse event. However, adverse events could still occur to participants, including adverse events not related to the study. Suicide or attempted suicide would be an example of an adverse event. SAEs will be reported to the Institutional Review Board, Data and Safety Monitoring Board and NIA representatives within 48 hours of the PI learning of the events. A report of all AEs will be sent to the Chair of the DSMB on a monthly basis.

### **Internal Data and Safety Monitoring Board (DSMB)**

This plan describes the monitoring activities of our internal DSMB. In addition to the activities of the DSMB, clinical monitoring is an ongoing process. These responsibilities are assumed by co-I and the Director of the Pacific Brain Health Center ([name]) and the clinical infrastructure of the Pacific Brain Health Center.

The DSMB will be comprised of Chair, [name], and [name] and [name]. The DSMB will meet initially prior to patient enrollment in the first year of the trial and then twice in subsequent years (2020, 2021) via conference call to monitor/audit the following, for a total of up to 3 calls during the course of this study:

1. Review all adverse event reports since the study initiation or since the last review will be reviewed at the DSMB meetings;
2. Review the medical record of all patients who have had a protocol-related serious adverse event since the last review;

3. Perform random audits of informed consent documents to verify that the informed consent procedures have been carried out and that necessary informed consent documents have been signed by study participants and staff;
4. Review data quality, completeness, and timeliness;
5. Review adequacy of compliance with goals for recruitment and retention, including those related to the participation of women and minorities;
6. Review adherence to the protocol;
7. Discuss factors that might affect the study outcome or compromise the confidentiality of the trial data (such as protocol violations);
8. Discuss factors external to the study such as scientific or therapeutic developments that may impact participant safety or the ethics of the study;
9. Follow up on problems previously identified

At the end of the meeting, the Principal Investigator, will summarize the findings of the DSMB and will subsequently implement recommendations for improvement in a timely manner. Special meetings of the DSMB may be convened when necessary, for urgent concerns regarding patient safety or data integrity. We don't anticipate that there will be many urgent patient concerns given the low risks associated with this trial.

#### **Definition of an AE**

The following definition of an adverse event (AE) will be used for this study:

- Any untoward medical occurrence in an enrolled subject who underwent procedures required by the study.

An AE can be any unfavorable and unintended sign, symptom, or disease (new or exacerbated) occurring after starting the procedures required by the study, even if the event is considered not related to the study procedures.

As far as possible, each adverse event will also be described by its duration (start and end dates), the intensity, its expectedness related to the known risks associated with the study procedures, and the action(s) taken.

It is the responsibility of the investigator to perform periodic and special assessments for AEs. The investigator and clinical staff will note all AEs reported by the subjects. All clinical complaints volunteered by, or elicited from, the subject during the study will be recorded separately on the appropriate page of the CRF. If any AE occurs, the subject will receive appropriate treatment and medical supervision if warranted.

All AEs judged to be clinically significant will be followed until resolution.

### **Definition of an SAE**

The definition of a serious adverse event (SAE) in this study is an AE that meets any of the following criteria:

- Results in death
- Is life-threatening

NOTE: The term 'life-threatening' in the definition of 'serious' refers to an event in which the subject was at risk of death at the time of the event. It does not refer to an event, which hypothetically might have caused death if it were more severe.

- Requires hospitalization or a prolongation of an existing hospitalization

NOTE: In general, hospitalization signifies that the subject has been detained at the hospital or emergency ward for observation or treatment that would not have been appropriate in the physician's office or outpatient setting. Complications that occur during hospitalization are AEs but not necessarily SAEs. An occurrence or complication that prolongs hospitalization is an SAE. When in doubt as to whether hospitalization occurred or was necessary, the AE should be considered an SAE. Hospitalization for elective treatments of a pre-existing condition that did not worsen from its original baseline is not considered an SAE.

- A persistent or significant disability or incapacity

NOTE: The term disability means a substantial disruption of a person's ability to conduct his/her regular life functions. This definition is not intended to include AEs of relatively minor medical significance such as uncomplicated headache, nausea, vomiting, diarrhea, influenza and accidental trauma (e.g., sprained ankle) which may interfere or prevent everyday life functions but do not constitute a substantial disruption.

- Other important medical event

NOTE: Medical or scientific judgment should be exercised in deciding whether reporting is appropriate for other important medical events that may not result in death, be life-threatening, or require hospitalization but still may jeopardize the subject or may require medical intervention to prevent one of the outcomes listed in this definition. These events should also be considered serious.

### **Recording AEs and SAEs**

If an AE or SAE occurs, and it is deemed related and unanticipated to this study, it is the responsibility of the PI to review all documentation (e.g., hospital progress notes, laboratory,

and diagnostic reports) relative to the event(s). The PI is to record all relevant information regarding any AE (including SAEs) on the AE page of the CRF. The PI will also attempt to establish a diagnosis of the event based on the signs, symptoms, or other clinical information. In such cases, the diagnosis, not the individual signs and symptoms, should be documented on the appropriate CRF as the AE or SAE.

### **Assessment of Intensity**

The PI will make an assessment of intensity for each AE and SAE reported during the study. The assessment will be based on the investigator's clinical judgment. The intensity of each AE recorded in the CRF should be assigned to one of the categories shown in Table 1.

**Table 1:** Classification of AEs by Intensity

Intensity	Definition
Mild AE	An event that is easily tolerated by the subject, causing minimal discomfort and not interfering with everyday activities.
Moderate AE	An event that is sufficiently discomforting, causing interference with normal everyday activities.
Severe AE	An event that prevents the subject from performing their everyday normal activities.

Any AE that changes in intensity or grade during its course will be recorded on the CRF at the highest-level experienced by the subject.

NOTE: An AE that is assessed as severe should not be confused with an SAE. Severity is a category utilized for rating the intensity of an event (such as mild, moderate, or severe myocardial infarction). However, the event itself may be of relatively minor medical significance (such as a severe headache), and both AE(s) and SAE(s) can be assessed as severe.

### **Expectedness of AEs**

An expected AE is one that is consistent with the known risk information associated with the study procedures.

An unexpected AE is defined, as any AE, the specificity or severity of which is not consistent with the known risk information. "Unexpected," as used in this definition, refers to an AE that has not been previously observed rather than from the perspective of such an AE not being anticipated based on the known effects of procedures required by the study.

### **Follow-Up of AEs and SAEs**

After the AE or SAE report, the PI will proactively follow each subject.

All AE(s) and SAE(s) will be followed until:

- Resolution

- The condition stabilizes
- The event is otherwise explained
- The subject is lost to follow-up

Once the event is resolved, the appropriate SAE report page will be updated. The PI will also ensure that the follow-up includes any supplemental information that may explain the causality of the event(s).

All SAEs will be reported to DSMB and NIH representatives within 48 hours of the PI learning about the SAE.

### Subject Anonymity

The anonymity of participating subjects must be maintained. Subjects will be identified by their initials and an assigned subject number on CRFs and other documents retrieved from the site or sent to the study monitor, sponsor, regulatory agencies or central laboratories/reviewers. Documents that identify the subject (e.g., the signed informed consent document) must be maintained in strict confidence by the investigator, except to the extent necessary to allow auditing by the appropriate authorities, the study monitor, or sponsor representatives.

**Table 1:** Classification of AEs by Intensity

Intensity	Definition
Mild AE	An event that is easily tolerated by the subject, causing minimal discomfort and not interfering with everyday activities.
Moderate AE	An event that is sufficiently discomforting, causing interference with normal everyday activities.
Severe AE	An event that prevents the subject from performing their everyday normal activities.

Any AE that changes in intensity or grade during its course will be recorded on the CRF at the highest-level experienced by the subject.

NOTE: An AE that is assessed as severe should not be confused with an SAE. Severity is a category utilized for rating the intensity of an event (such as mild, moderate, or severe

myocardial infarction. However, the event itself may be of relatively minor medical significance, such as a severe headache), and both AE(s) and SAE(s) can be assessed as severe.

Although subjects will be encouraged to complete the study, they may voluntarily withdraw at any time. The investigator will document the reasons for discontinuation.

## **10. SUBJECT DISCONTINUATION AND TERMINATION OF STUDY**

Although subjects will be encouraged to complete the study, they may voluntarily withdraw at any time. The investigator will document the reasons for discontinuation.

Also the investigator may withdraw the subject from the study. The subject will be removed from the study without their consent for various health, safety or administrative reasons, including but not limited to the following:

- The investigator decides that continuing in the study would be harmful to subject.
- The sponsor cancels the study.
- Other administrative reasons.

The investigator will make the decision and let the subject know if it is not possible for him/her to participate.

## **11. COVID-19 PRECAUTIONS**

If needed, depending on the status of the coronavirus pandemic, precautions may be taken to limit the risk of transmitting COVID-19 via study procedures per our institutional policies (Providence Health). Study visits including intake, neuropsychological evaluation at the discretion of the clinician, and physical status assessments may be done using remote procedures. In order to collect physical status assessments, study equipment such as a blood pressure cuff and a calibrated scale may be sent to the participant's home. The participant will be responsible for returning any additional study equipment. Although all COVID-19 related healthy and safety precautions will be addressed throughout this study, some participants may still not be willing to come on-site to PBHC to undergo the mSIM on-boarding session. In this instance then there will be an option for the study staff to perform this in-person visit at their home. Remote visits may continue after the COVID-19 crisis if deemed necessary by the PI or DSMB to preserve the integrity of the research study data. Some study participants may want to further minimize on-site activity. During COVID, participants may request to skip the MRI or QEEG assessments. The following precautions for any in-person study visits may be employed based on the discretion of the PI and institutional policies: screening of participants with questions regarding COVID-19 symptoms/exposure, temperature checks prior to in-person visits, physical distancing as much as possible during the visit, use of personal protective equipment (e.g. masks) during in-person visits, or pre-visit COVID-19 testing.

If a study participant tests positive for COVID-19 and cannot exercise, they may pause participation in the study. They can re-initiate in the study where they left off and the timeline will be paused for up to four weeks and depending on the severity of the case. Participants

Sponsor: National Institute of Health (NIH)

Protocol #: mSIM (NIH 1R21AG061494-01)

Version #/Date: Ver. 04/26-Oct-2021

will be asked to provide medical clearance to re-initiate into the study. The participant may be asked to ramp up exercise for up to 2 weeks at the discretion of the PI and DSMB. If the participant requires more than 4 weeks to re-initiate into the protocol, they will be terminated from the study at that time.

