## **6. ANALYTICAL METHODS**

To determine feasibility of the protocol, we will analyze adherence and feasibility data from participants via a secure data-aggregation program from which will pull de-identified FitBit session data and also from the session dashboard profiles from the mSIM web-based application. During the intervention, we will collect data related to program adherence in the mSIM web-based application.

In order to determine whether the mSIM treatment protocol produces significant improvements in cognitive abilities, our primary analytic tool will be the linear regression model, which will be implemented as an ANCOVA in SPSS or similarly capable statistical software (e.g., R statistical software and SAS). Outcomes will be the post-trial assessment measurements, baseline measurements of the outcomes will be used as covariates, and treatment group (Group 2 (mSIM) or Group 1 (CON)) will be the key variable to assess the treatment effect.

We will also perform an analysis of peripheral biomarker data to help us understand the biological underpinnings of any cognitive changes produced by the mSIM treatment protocol. Outcomes will be the post-trial biomarker measurements of BDNF or NE corrected concentration levels, baseline measurements of BDNF or NE corrected concentration levels will be used as covariates, and treatment group (Group 2 (mSIM) or Group 1 (CON)) will be the

key variable to assess the treatment effect. We will also conduct an exploratory analysis where we will evaluate the extent to which changes in BDNF and NE separately relate to changes in memory performance (composite memory Z-score) through correlational analyses.

To quantify the effects of the mSIM intervention on cognitive inhibitory tone, we will perform an analysis of the QEEG data. Our primary indicator is a metric called peak Alpha frequency. Outcomes will be the post-trial peak alpha frequency, baseline measurements peak alpha frequency will be used as covariates, and treatment group (Group 2 (mSIM) or Group 1 (CON)) will be the key variable to assess the treatment effect. We will also conduct an exploratory analysis where we will evaluate the extent to which changes in peak alpha frequency separately relate to changes in memory performance (composite memory Z-score) or other biomarker data through correlational analyses. Additional metrics from the QEEG will be explored. EEG will be provided in-kind by Evox and not the NIA-funded study.

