### **APPENDIX I. STUDY TIMELINE (IN MONTHS) THE MSIM TRIAL RCT**

Each participant (N=30) will be enrolled for up to 26 weeks (6 months). Participants in the active arm (N=15, Group 2) arm will have the “mSIM Intervention” sessions outlined below, and patients in the control arm will only have activity monitoring via FitBit device. Group 1 will be granted access to the mSIM web-application after completing the intervention.

	Screen	Randmz.	Baseline	1 Mo	2 Mo	3 Mo	4 Mo	5 Mo	6 Mo	Post-Trial
Visit Window	-30 to -1 days	+/- 7 days	+/- 7 days	+/- 7 days	+/- 7 days	+/- 7 days	+/- 7 days	+/- 7 days	+/- 7 days	
*Consent & screening	1x									
*Intake questionnaires and assessments	1x									
Medical Clearance to Exercise	1x									
Randomization		1x								
Credit card authorization			1x							
Physical status assessment			1x						1x	
Lifestyle and/or satisfaction data			1x				1x	1x		
mSIM Intervention (Group 2 (SIM))										
Equipment instruction			1x							
Equipment drop-off			1x							
Equipment pick-up								1x		
Exercise ramp-up session				4-12x (2-6 weeks duration)						
Gain access to mSIM web-app						✓				
Virtual Support Sessions						✓				
mSIM exercise session				24 x (12-14 weeks duration)						
mSIM homework				24x (12-14 weeks duration)						
mSIM Intervention (Group 1 (CON))										
Access to mSIM web-app										1x
On-going Data Collection										
Fitbit					✓					
Imaging Data Collection										
QEEG			1x					1x		
MRI*			*1x					*1x		
Biological Sample Collection										
Blood sample			1x					1x		
Neuropsychological/Cognitive Assessments										
Virtual neuropsychological assessment	1x						1x	1x		

Notes: #x indicates the number of times a test or an intervention will occur in protocol window (e.g. 2x = two times). \*In participants that are eligible for an MRI.

✓ indicates ongoing data collection.

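### A participant who skips only the baseline QEEG drops out of the peak alpha ANCOVA although the post-trial value exists; the loss is probably small, and a model that keeps the value costs little.

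*Combined protocol and SAP*

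**What the plan says.** Section 11 (COVID-19 Precautions) foresees that "Some study participants may want to further minimize on-site activity" and then allows: "During COVID, participants may request to skip the MRI or QEEG assessments". The permission names no visit, and no rescheduling rule follows it.

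QEEG is recorded twice only, at baseline and post-trial (Section 3, Data Collection and Assessments; Appendix I). Section 3 lists randomisation first among the baseline procedures, and Appendix I gives it a column before Baseline. Enrolment is up to 30 participants, 15 per arm (Section 3, Subject Identification and Recruitment).

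Section 6 says of the QEEG data: "Our primary indicator is a metric called peak Alpha frequency". The model is set out as: "Outcomes will be the post-trial peak alpha frequency, baseline measurements peak alpha frequency will be used as covariates, and treatment group" as the variable of interest. The general method in that section is: "our primary analytic tool will be the linear regression model, which will be implemented as an ANCOVA in SPSS or similarly capable statistical software". An exploratory analysis asks how far "changes in peak alpha frequency separately relate to changes in memory performance (composite memory Z-score) or other biomarker data through correlational analyses". Neither section states a missing-data method, a QEEG analysis set or a rule for a missing baseline.

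**The concern.** The protocol itself makes missing QEEG a foreseen event, yet the model in Section 6 needs both recordings from each person. Someone who skips the baseline recording and attends the post-trial one supplies a randomised outcome that the ANCOVA cannot use.

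Peak alpha is the lead QEEG measure and belongs to the third major objective in Section 2. With at most 15 per arm, each discarded outcome costs some precision. In addition, the analysed subset is formed partly by requests that can be made after the arm is known: mSIM participants are given a bike, a tablet and a binder, so allocation is evident to them.

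**Working it through.** The plan gives no power, effect size, standard deviation, baseline/post correlation or skip rate for QEEG, so there is no stated figure to reproduce. The skip rate, its pattern and the correlation below are assumptions.

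**Counts.** Let N = 30, let p be the chance of skipping a given visit, and let q be the share of those skipping one visit who also skip the other.

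- Post-trial recordings collected: N(1 − p).
- Of these, without a baseline: N·p·(1 − q).
- Share left unused: p(1 − q)/(1 − p).

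Independent skipping is the case q = p. With p = 0.20, 30 × 0.80 = 24 post-trial recordings are collected.

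**Precision.** Simulations used 15 per arm, bivariate normal baseline and post-trial values, and skipping at random. The last column is the standard error of the constrained longitudinal model divided by that of the complete-case ANCOVA, over correlations 0.5 to 0.8.

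| Pattern at p = 0.20 | Unused post-trial values | Share of 24 | SE ratio |
|---|---|---|---|
| Independent (q = 0.20) | 30 × 0.20 × 0.80 = 4.8 | 20% | 0.89–0.91 at correlation 0.5; 0.92–0.94 at 0.7; 0.94–0.97 at 0.8 |
| Half skip both (q = 0.50) | 30 × 0.20 × 0.50 = 3.0 | 12.5% | 0.96–0.98 |
| 80% skip both (q = 0.80) | 30 × 0.20 × 0.20 = 1.2 | 5% | 0.97–1.00 |
| All skip both (q = 1) | 0 | 0% | 1.00 |

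Repeat runs of the same setting differed by up to 0.03, so these percentages are approximate. At correlation 0.9 with independent 20% skipping the ratio was 0.97.

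**Other rates, independent skipping.** At 10% the ratios were 0.96, 0.96–0.97 and 0.98 at correlations 0.5, 0.7 and 0.8. At 30% they were 0.83–0.84, 0.88–0.89 and 0.91–0.95. At 10% with half of skippers missing both visits they were 0.98, 0.98 and 0.99.

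**Bias.** Under random skipping both estimators were unbiased. No bias was calculated for skipping that depends on arm or outcome, because the documents give nothing on which to base it.

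**A simpler repair.** Filling the missing baseline with the mean and adding a missing indicator also keeps the post-trial value. The test case had 20% of baselines skipped, no post-trial skips, a 0.8 SD effect and two-sided 5%. At correlation 0.5, power was 67% with full data, 57% complete-case and 64% with the repair. At correlation 0.8 it was 93%, 87% and 84%, so there the repair did worse than dropping the cases. Type I error stayed near 5% throughout.

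**The case against.** The strongest reply is that the loss may hardly arise. The reason Section 11 gives is a preference for less on-site activity, which could well apply to both visits. A person who skips both has no post-trial value to discard. A reader might infer from the first row of the table that one in five post-trial recordings will be lost, but that follows only from assuming independent skips at 20%, and the documents support neither the rate nor the independence. The permission is also limited to the pandemic. This stands, and it is why the size is given as a range that reaches zero.

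A reader might also infer that the comparison between arms is biased. The documents do not show this. The order of randomisation and baseline QEEG makes differential skipping possible, and mSIM has an on-boarding visit that the control arm lacks. But Section 11 allows that visit at home, and both arms have other baseline assessments, such as the blood draw.

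Nor do the documents say that such participants will be excluded. Exclusion is what an ordinary ANCOVA does when a covariate is missing and nothing else is specified.

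Finally, this is a pilot, QEEG is provided in kind outside the funded study, and the coverage and type I error of the longitudinal model at this sample size were not examined. These points limit the priority. They do not remove the gap, because a post-trial value without a baseline has no place in the model as written.

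**Conclusion.** The gap is real and modest. As specified, the peak alpha ANCOVA leaves out people who skipped only the baseline QEEG, and nothing in Section 6 or Section 11 deals with this. If 20% skip each visit, keeping their post-trial values would cut the standard error by about 3 to 10% under independent skipping, about 1 to 4% if half of skippers miss both visits, and close to nothing if nearly all do. Gains are smaller at lower skip rates and at higher baseline/post correlations. All of this rests on assumed rates and on skipping at random.

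Under random skipping the issue is precision, not validity. Differential skipping by arm is a possibility to guard against, not an established fault. The cognitive ANCOVAs are untouched. The same permission covers MRI, which is exploratory. The point is one to consider; it does not undermine the trial.

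**What to change.** 1. **Section 6.** Analyse peak alpha with a constrained longitudinal model: baseline and post-trial values both as responses, a common baseline mean for the two arms, an unstructured covariance and a small-sample degrees-of-freedom correction. Include everyone with at least one recording, and keep the complete-case ANCOVA as a sensitivity analysis. With complete data the model gives essentially the ANCOVA estimate, so little is lost if nobody skips.
2. **Section 11.** Ask for and record any wish to skip QEEG or MRI before randomisation, and report skips by arm, visit and reason.

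The limits should be stated. Asking early limits selection after allocation and makes it visible, but does not remove it, since a participant can still change their mind later. A skipped post-trial value is handled only under a missing-at-random assumption, and a person with no recording contributes nothing. The exploratory change correlations will still need both recordings.

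The cost is wording in two sections and a slightly more complex model, which the software already named in Section 6 can fit. No extra visits or participants are needed.
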